16.2.2.4. Analysis of the Primary Endpoint

The population for the primary endpoint analysis will be subjects in the ITT population with a baseline and at least one post-baseline CDR-SB score. A mixed model repeated measures (MMRM) model will be used as the primary analysis to analyze change from baseline CDR-SB using fixed effects of treatment, time, treatment-by-time interaction, baseline CDR-SB, baseline CDR-SB by time, baseline MMSE, and baseline ApoE ε4 status.

CONFIDENTIAL

The information contained herein may not be used, disclosed, or published without the written consent of Biogen MA Inc.

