16.7. Sample Size Considerations

The study's sample size is based, in part, on results from a protocol-specified interim analysis from Study 221AD103 which included 1 year data from 1, 3 and 10 mg/kg treatment groups.

A sample size of 450 subjects per treatment group will have approximately 90% power to detect a true mean difference of 0.5 in change from baseline CDR-SB at Week 78 between the 2 treatment groups. This power calculation is based on a 2-sided t-test assuming equal variance with a final significance level of 0.05, a SD of 1.92 and a drop-out rate of 30%. The SD estimate of 1.92 for Week 78 reflects a 39% increase over the SD from the protocol-specified interim analysis of 1-year data.

CONFIDENTIAL

The information contained herein may not be used, disclosed, or published without the written consent of Biogen MA Inc.

The assumed true mean difference of 0.5 between the 2 treatment groups represents an approximately 25% reduction in the placebo mean change from baseline at Week 78 if the placebo mean change is estimated to be 2.

The sample size may be reassessed in a blinded manner approximately 3 months before enrollment is complete if at least 15% of the data are available on the primary endpoint. At this interim time-point, the SD for the primary endpoint will be estimated based on the blinded data. The sample size may be increased if the SD is estimated to be more than approximately 2.07. In addition, the sample size could be increased using external clinical trial results that become available after the start of the study.

CONFIDENTIAL

The information contained herein may not be used, disclosed, or published without the written consent of Biogen MA Inc.

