7. STUDY DESIGN

7.1. Study Overview

Study 221AD302 is a multicenter, randomized, double-blind, placebo-controlled, parallel-group study in subjects with early AD, including MCI due to AD and a subset of mild AD, followed by an optional 24-month dose-blind LTE study. Approximately 1350 subjects will be enrolled across approximately 150 centers globally. The primary study objective is to evaluate the efficacy of monthly doses of aducanumab on the CDR-SB relative to placebo. Secondary objectives include assessment of the effect of monthly doses of aducanumab on clinical progression as compared to placebo. The safety of monthly doses of aducanumab will also be evaluated.

Subjects will receive infusions of aducanumab or placebo approximately every 4 weeks for approximately 18 months (a total of 20 doses). Subjects will be randomized to receive aducanumab low dose: aducanumab high dose: placebo in a 1:1:1 ratio. The randomization will be stratified by site and ApoE ϵ 4 status (carrier or non-carrier). Subject enrollment will be monitored so that approximately 60% to 70% ApoE ϵ 4 carriers are enrolled. Enrollment will also be monitored, via interactive response technology (IRT), such that subjects with mild AD represent a small percentage of the total enrolled in the trial.

At the end of the double-blind, placebo-controlled treatment period, subjects who meet the extension entry criteria may enter a 24-month long-term safety and efficacy extension period, with all subjects receiving aducanumab approximately every 4 weeks (a total of 26 doses).

The total duration of study participation for each subject only participating in the placebo-controlled period of the study will be up to approximately 102 weeks, including a series of Screening visits within 8 weeks before administration of the first dose, a 76-week placebo-controlled treatment period, and a safety follow-up (FU) period of approximately 18 weeks after the final dose.

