9.2. Randomization and Registration of Subjects

Subjects will be registered at the Screening Visit and randomized only after all baseline assessments have been completed and the Investigator has verified that the subjects are eligible per criteria in Sections 8.1 and 8.2. No subject may begin treatment prior to assignment of a unique identification number (registration) and randomization. Any subject identification numbers or randomization schedule assignments that are assigned will not be reused even if the subject does not receive treatment. Rescreened subjects will be assigned a new number.

Subjects will be randomized to receive aducanumab low dose; aducanumab high dose; placebo in a 1:1:1 ratio. The randomization will be stratified by site and ApoE ϵ 4 status (carrier or non-carrier), so that approximately 60% to 70% ApoE ϵ 4 carriers are enrolled. Enrollment will also be monitored, via the IRT, such that the population of subjects with mild AD represents a small percentage of the total enrolled in the trial. Subjects who withdraw from the study may not be replaced.

Refer to the Study Reference Guide for details on registration and randomization.

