11.5.1.1. Allowed Concomitant Therapy

- Medications for chronic conditions are allowed at a stable dose during the study as long as the subject has been stable on the medication(s) for at least 4 weeks prior to Screening Visit 1.
- Symptomatic therapies for AD, including but not limited to donepezil, rivastigmine, galantamine, tacrine, and memantine, are allowed provided that subjects are receiving a stable dose for at least 8 weeks prior to Screening Visit 1 and that they stay on a stable dose while in the study.
- Vaccinations with live or attenuated vaccines are allowed during the study. Administration of any vaccination/booster should not be given <10 days prior to any dosing visit and for 10 days after a dosing visit.

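### The primary and secondary MMRMs have no term for site or geography although randomisation is stratified by site: at most a small loss of precision, cheaply avoided

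*Protocol*

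**What the plan says.** On randomisation, Protocol version 3.0, Section 9.2, reads "The randomization will be stratified by site and ApoE" ε4 status, with allocation to low dose, high dose and "placebo in a 1:1:1 ratio". Section 7.1 repeats the two factors and gives the scale: "Approximately 1350 subjects will be enrolled across approximately 150 centers globally". Region is not named as a factor anywhere.

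On analysis, Section 16.2.2.4 gives the primary MMRM as "fixed effects of treatment, time, treatment-by-time interaction, baseline CDR-SB, baseline CDR-SB by time, baseline MMSE, and baseline ApoE" ε4 status. The list is the same in version 3.0 and in the later text of Section 16 at the front of the file. Section 16.2.2.5 builds the MMSE, ADAS-Cog 13 and ADCS-ADL-MCI models in the same way: own baseline, its interaction with time, ApoE ε4 status and, for the last two, baseline MMSE. No model has a site, pooled-site or region term. The protocol gives no reason for this and, for these covariate lists, does not defer to the SAP.

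On AD medication, Section 11.5.1.1 says "Symptomatic therapies for AD, including but not limited to donepezil, rivastigmine, galantamine, tacrine, and memantine, are allowed" at a stable dose. Section 11.5.1 has prior AD medication over the 12 months before Screening recorded, and treats any drug taken from consent onward as concomitant therapy. Baseline use is therefore known for every subject, but it is not a covariate.

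**The concern.** When arms are balanced on a factor by design, chance differences between arms on that factor are largely removed. If the factor predicts outcome and the model ignores it, its variation stays in the residual. The reported standard error then overstates the true sampling variability of the treatment difference, so the test is conservative and the confidence interval wider than it need be. Here the ignored factor is site. In a trial of about 150 centres worldwide, with CDR scored by raters designated at each site, some site or geographic component of CDR-SB change is plausible, though the documents do not measure it.

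Baseline AD medication is a different case, because it is not a randomisation factor. Leaving it out does not make the standard error wrong. It only forgoes whatever variance medication use would explain.

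What is at stake is efficiency on the primary contrast and on the secondary endpoints that use the same structure.

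**Working it through.** **Inputs** (Section 16.7 unless noted): 450 subjects per arm; difference 0.5 CDR-SB points at Week 78; SD 1.92; two-sided alpha 0.05; drop-out 30%; a t-test with equal variances and no stated covariates. Section 7.1: about 1350 subjects and 150 sites. The share of residual variance explained by added covariates (R²) is not in the documents. I assume 0 to 5%.

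**Step 1: reproduce the stated power.** The plan states "A sample size of 450 subjects per treatment group will have approximately 90% power" for a "true mean difference of 0.5 in change from baseline CDR-SB at Week 78", and says "This power calculation is based on a 2-sided t-test assuming equal variance".

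- Evaluable per arm: 450 × 0.70 = 315.
- SE = 1.92 × √(2/315) = 0.153.
- Power by noncentral t: 90.4% (normal approximation 90.5%).
- In reverse, 90% power needs 310 evaluable per arm, and 310/0.70 ≈ 443, close to 450.

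The stated figure reproduces.

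**Step 2: effect of adding a few useful covariates.** Residual SD becomes 1.92 × √(1 − R²). The cost in degrees of freedom is negligible with several hundred subjects.

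| Assumed R² | SD | SE | SE reduction | Power (noncentral t) |
|---|---|---|---|---|
| 0% | 1.920 | 0.153 | 0% | 90.4% |
| 1% | 1.910 | 0.152 | 0.5% | 90.7% |
| 2% | 1.901 | 0.151 | 1.0% | 90.9% |
| 3% | 1.891 | 0.151 | 1.5% | 91.2% |
| 5% | 1.871 | 0.149 | 2.5% | 91.7% |

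Expressed as evaluable subjects per arm, the gain is 315/(1 − R²) − 315: about 6 at R² = 2% and about 17 at R² = 5%.

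**Step 3: why site should not be fitted as it stands.** 1350/150 = 9 subjects per site, or 3 per arm per site. Crossed with ApoE status, 1350/(150 × 2) = 4.5 subjects per stratum. Simulated designs (60 replicates; 30% random drop-out; assumed blocks of 3 within site and ApoE stratum; 65% carriers; equal or skewed site sizes) show that fixed site effects multiply the variance of the high-dose versus placebo contrast by 1.075 to 1.080.

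- Break-even R² for site: 1 − 1/1.075 ≈ 7.0% to 1 − 1/1.080 ≈ 7.4%.
- If site explains nothing, SE = 0.153 × √1.075 ≈ 0.159 and power falls to about 88% (normal approximation).

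So fixed site effects help only if site explains more than about 7% of residual variance. A region term with a handful of levels does not carry that cost.

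**The case against.** **Only site is a randomisation factor.** A reader might infer that the model drops region as a stratification factor. The documents do not support that. Stratifying by site does tend to balance any region built from whole sites, so a region term respects the design, but nothing shows that region predicts CDR-SB change. Leaving out about 150 fixed site effects is itself defensible, as Step 3 shows.

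**The model already holds strong candidates.** Baseline CDR-SB, its interaction with time, baseline MMSE and ApoE ε4 status are all in it. A reader might infer that known predictors have been ignored. The protocol does not establish that baseline AD medication or clinical stage predicts progression. It asks for stable dosing and for assessments before any change in AD medication, which shows caution about changes rather than evidence on baseline use. Stage has little room to add information: mild AD is kept to a small share, and entry requires a CDR global score of 0.5 and MMSE of 24 to 30. The case for letting ApoE and MMSE interact with visit is likewise an assumption.

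**The reference power is not that of the planned model.** The 90.4% comes from an unadjusted t-test on 315 per arm. The MMRM adjusts for baseline and uses partial data from subjects who drop out after a post-baseline score, so its power may already be higher, with less left to gain.

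**The record is incomplete.** The randomisation section matching the latest text of Section 16 is not shown, nor is the SAP, which may add covariates.

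These points limit the size and certainty of the gain. They do not remove the mismatch: within version 3.0 itself, randomisation uses site and ApoE while the stated models use ApoE alone, without explanation.

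**Conclusion.** The point holds as a modest matter of efficiency. The primary and secondary MMRMs omit one of the two randomisation factors and put nothing in its place. If outcome varies by geography, the standard error is somewhat conservative. Under the assumed R² of 0 to 5%, the SE falls by 0 to 2.5% and power rises from about 90.4% to at most about 91.7%. The gain may be close to zero.

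A reader might go further and conclude that the trial is underpowered, the estimate biased or the type I error inflated. None of these follows. The stated power reproduces without relying on any covariate, randomisation protects the estimate, and ignoring a balanced factor pushes the test towards caution.

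The omission is certain for version 3.0. That it carries over to the later version assumes that the stratification factors were not changed. The size of the gain rests wholly on the assumed R².

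**What to change.** In Sections 16.2.2.4 and 16.2.2.5, add two fixed effects to each model: region, as a pooling of sites whose definition is fixed before unblinding, and baseline symptomatic AD medication use (yes/no). State that individual sites will not be fitted as fixed effects, and why. Clinical stage (MCI or mild AD) and interactions of ApoE ε4 status and baseline MMSE with visit are optional. If the sponsor prefers the present list, one sentence justifying the absence of any site or region term would close the point.

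The cost is wording, a pooling rule and a few degrees of freedom. Site is known and medication is already recorded, so no new data are needed and the sample size does not change.

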16.2.2.5. Analysis of the Secondary Endpoints

16.2.2.5.1. Change From Baseline to Week 78 in MMSE

The population for the analysis will be subjects in the ITT population with a baseline and at least one post-baseline MMSE value. A MMRM model will be used as the primary analysis to analyze change from baseline MMSE using fixed effects of treatment, time, treatment-by-time interaction, baseline MMSE value, baseline MMSE by time interaction and baseline ApoE $\epsilon 4$ status.

16.2.2.5.2. Change From Baseline to Week 78 in ADAS-Cog 13

The population will be subjects in the ITT population with a baseline and at least one post-baseline ADAS-Cog 13 score. An MMRM model will be used as the primary analysis to analyze change from baseline ADAS-Cog 13 using fixed effects of treatment, time, treatment-by-time interaction, baseline ADAS-Cog 13, baseline ADAS-Cog 13 by time interaction; baseline MMSE, and baseline ApoE $\epsilon 4$ status.

16.2.2.5.3. Change From Baseline to Week 78 in ADCS-ADL-MCI

The population will be subjects in the ITT population with a baseline and at least one post-baseline ADCS-ADL-MCI score. An MMRM model will be used as the primary analysis to analyze change from baseline ADCS-ADL-MCI using fixed effects of treatment, time, treatment-by-time interaction, baseline ADCS-ADL-MCI, baseline ADCS-ADL-MCI by time interaction; baseline MMSE, and baseline ApoE $\epsilon 4$ status.

16.2.2.6. Tertiary Endpoints Analysis

16.2.2.6.1. Placebo-Controlled Period

Where appropriate, a MMRM model will be used as the primary analysis to analyze change from baseline using fixed effects of treatment, time, treatment by time interaction, baseline value, baseline value by time interaction, baseline MMSE and baseline ApoE $\epsilon 4$ status.

Otherwise, an analysis of covariance or its non-parametric equivalent may be used to analyze these exploratory endpoints.

16.2.2.6.2. Long-Term Extension Period

The additional endpoints for the LTE period are change from baseline over the placebo-controlled and LTE periods of the study. Analyses will be presented by treatment group in the placebo-controlled period using the placebo-controlled period baseline. Details of the analyses will be pre-specified in the SAP.

16.3. Pharmacokinetics

16.3.1. Analysis Population

The population for PK analysis is defined as all subjects who were randomized, were dosed with study treatment, and had at least 1 measurable aducanumab concentration in serum.

CONFIDENTIAL

The information contained herein may not be used, disclosed, or published without the written consent of
Biogen MA Inc.

16.3.2. Method of Analysis

The population PK characteristics of aducanumab will be determined by nonlinear mixed effects approach. Covariates that might influence the disposition of aducanumab (e.g., body weight, age, sex, immunogenicity, ApoE ε4 status) will be evaluated and the potential exposure-response relationships will be explored.

16.4. Safety

16.4.1. Analysis Population

The safety population is defined as all subjects who received at least 1 dose of study treatment (including placebo and aducanumab).

16.4.2. Methods of Analysis

All AEs, laboratory data, ECG, neurological and physical examinations and vital signs will be evaluated for safety.

16.4.2.1. Adverse Events

Only treatment-emergent adverse events (TEAEs) will be presented in the summary tables. Treatment emergent is defined as having an onset date that is on or after the start of study treatment, or as worsening after the start of study treatment.

Incidence of TEAEs will be summarized by treatment groups, overall, by severity, and by relationship to study treatment for the placebo-controlled period and over the 24-month LTE period. The summary tables will include incidence estimates for overall system organ class as well as for preferred terms within each system organ class. AEs will be coded using the Medical Dictionary for Regulatory Activities (MedDRA).

16.4.2.2. Clinical Laboratory Results

Laboratory data will be summarized using shift tables. Shifts from baseline to high/low status for hematology and blood chemistry parameters, and shifts from baseline to high/positive status for urinalysis will be presented. In addition, the shift from baseline to the maximum post-baseline value and the shift from baseline to the minimum post-baseline status will be presented for each laboratory test by treatment group. Also, summaries of laboratory values categorized based on common toxicity criteria grade will be created. Summary statistics for actual values and change from baseline will also be presented for quantitative laboratory data.

16.4.2.3. Vital Signs

The analysis of vital signs will focus on clinically relevant abnormalities.

16.4.2.4. ECG

The number and percentage of subjects with shifts to categorical values (abnormal not AE, or abnormal AE) will be summarized by treatment group.

CONFIDENTIAL

The information contained herein may not be used, disclosed, or published without the written consent of Biogen MA Inc.

16.4.2.5. Columbia Suicide Severity Rating Scale

The Columbia Suicide Severity Rating Scale data will be summarized by treatment group.

16.5. Immunogenicity Data

16.5.1. Analysis Population

The analysis population for immunogenicity is defined as all subjects in the safety population who have at least 1 post-dose sample evaluated for immunogenicity.

16.5.2. Methods of Analysis

Anti-aducanumab serum antibodies will be summarized using shift tables.

16.6. Interim Analyses

16.6.1. Interim Futility Analysis

An interim analysis for futility of the primary endpoint will occur after approximately 50% of the subjects have completed the Week 78 Visit (or discontinued). In order to maintain the treatment blind, an independent group external to Biogen that will not be involved in the conduct of the study after unblinding will perform the interim futility analysis. This independent group will present the unblinded interim analysis to the IDMC. The IDMC may recommend terminating the study for futility if it is evident that the efficacy of aducanumab is unlikely to be achieved.

The futility criteria will be discussed in detail in the SAP.

16.6.2. Interim Superiority Analysis

An interim analysis for superiority may be performed after approximately 50% of the subjects have completed the Week 78 Visit (or discontinued). The O'Brien-Fleming boundary approach will be used for the analysis. In order to maintain the treatment blind in the event of this interim analysis, an independent group external to Biogen that will not be involved in the conduct of the study after unblinding will perform the interim superiority analysis. The independent group will present the unblinded interim analysis to the IDMC. The aim of this interim analysis is to allow the possibility to demonstrate treatment effect early. The analysis will be discussed in detail in the SAP.

16.7. Sample Size Considerations

The study's sample size is based, in part, on results from a protocol-specified interim analysis from Study 221AD103 which included 1 year data from 1, 3 and 10 mg/kg treatment groups.

A sample size of 450 subjects per treatment group will have approximately 90% power to detect a true mean difference of 0.5 in change from baseline CDR-SB at Week 78 between the 2 treatment groups. This power calculation is based on a 2-sided t-test assuming equal variance with a final significance level of 0.05, a SD of 1.92 and a drop-out rate of 30%. The SD estimate of 1.92 for Week 78 reflects a 39% increase over the SD from the protocol-specified interim analysis of 1-year data.

CONFIDENTIAL

The information contained herein may not be used, disclosed, or published without the written consent of Biogen MA Inc.

The assumed true mean difference of 0.5 between the 2 treatment groups represents an approximately 25% reduction in the placebo mean change from baseline at Week 78 if the placebo mean change is estimated to be 2.

The sample size may be reassessed in a blinded manner approximately 3 months before enrollment is complete if at least 15% of the data are available on the primary endpoint. At this interim time-point, the SD for the primary endpoint will be estimated based on the blinded data. The sample size may be increased if the SD is estimated to be more than approximately 2.07. In addition, the sample size could be increased using external clinical trial results that become available after the start of the study.

CONFIDENTIAL

The information contained herein may not be used, disclosed, or published without the written consent of Biogen MA Inc.

17. ETHICAL REQUIREMENTS

Biogen, [REDACTED], and the Investigator must comply with all instructions, regulations, and agreements in this protocol and applicable International Conference on Harmonisation (ICH) and Good Clinical Practice (GCP) guidelines and conduct the study according to local regulations.

The Investigator may delegate responsibilities for study-related tasks where appropriate to individuals sufficiently qualified by education, training, and experience, in accordance with applicable ICH and GCP guidelines. The Investigator should maintain a list of the appropriately qualified persons to whom significant study-related duties have been delegated.

17.1. Declaration of Helsinki

This study will be performed in alignment with the ethical principles outlined in the Declaration of Helsinki.

